#### **14.5 Disclosure and Publication Policy**

All information provided regarding the study, as well as all information collected/documentated during the course of the study, will be regarded as confidential. The Sponsor reserves the right to release literature publications based on the results of the study. Results from the study will be published/presented as per the Sponsor's publication process.

Inclusion of the Investigator in the authorship of any multi-center publication will be based upon substantial contribution to the study design, the analysis or interpretation of data, or the drafting and/or critically revising of any manuscript(s) derived from the study. The Investigator acknowledges that the study is part of a multi-center study and agrees that any publication by the Investigator of the results of the study conducted at the research site shall not be made before the first multi-center publication. In the event there is no multi-center publication within fifteen (15) months after the study has been completed or terminated at all study sites and all data have been received, the Investigator shall have the right to publish his/her results from the study, subject to the notice requirements described herein and subject to acknowledgement of the Sponsor as appropriate. The Investigator shall provide the Sponsor thirty (30) days to review a manuscript or any poster presentation, abstract or other written or oral material that describes the results of the study for the purpose only of determining if any confidential or patentable information is disclosed thereby. If the Sponsor requests in writing, the Investigator shall withhold any publication or presentation an additional sixty (60) days solely to permit the Sponsor to seek patent protection and to remove any Development Innovations confidential information from all publications.

*CONFIDENTIAL*

Study Drug: AC176

Sponsor/Development Innovations Study Number: AC176-001/GU 207

Final Protocol: 10 July 2023 Version 4.0

## 16. APPENDICES

### Appendix A: Eastern Cooperative Oncology Group (ECOG) Performance Status Criteria

ECOG Performance Status Scale	
Grade	Descriptions
0	Normal activity. Fully active, able to carry on all pre-disease performance without restriction.
1	Symptoms, but ambulatory. Restricted in physically strenuous activity, but ambulatory and able to carry out work of a light or sedentary nature (e.g., light housework, office work).
2	In bed <50% of the time. Ambulatory and capable of all self-care, but unable to carry out any work activities. Up and about more than 50% of waking hours.
3	In bed >50% of the time. Capable of only limited self-care, confined to bed or chair more than 50% of waking hours.
4	100% bedridden. Completely disabled. Cannot carry on any self-care. Totally confined to bed or chair.
5	Dead

**Appendix B: Guidelines for Evaluation of Objective Tumor Response Using RECIST  
Version 1.1 (Response Evaluation Criteria in Solid Tumors) in Soft Tissue  
and PCWG3 (Prostate Cancer Working Group Criteria 3) in Bone Lesions**

**Introduction**

This appendix details the general implementation of RECIST v1.1 (Response Evaluation Criteria in Solid Tumors version 1.1) guidelines (Eisenhauer et al 2009) for the study with regards to Investigator assessment of tumor burden and PCWG3 guidelines (Scher et al. 2016).

**Definition of Measurable and Non-measurable Lesions**

**Measurable:**

*Tumor lesions:* To be considered measurable disease, tumor lesions must be accurately measured in at least 1 dimension (longest diameter in the plane of measurement is to be recorded) with a minimum size of:

- 10 mm by computed tomography (CT scan slice thickness/interval no greater than 5 mm); up to 5 lesions (with a maximum of 2 lesions per organ) per **PCWG3**
- 10 mm caliper measurement by clinical exam (lesions which cannot be accurately measured with calipers should be recorded as non-measurable)
- 20 mm by chest X-ray

*Malignant lymph nodes:* To be considered pathologically enlarged and measurable, a lymph node must be  $\geq 15$  mm in short axis when assessed by CT scan (CT scan slice thickness recommended to be no greater than 5 mm). At baseline and in follow-up, only the short axis will be measured and followed. Per **PCWG3** - Nodal disease should be measured in the short axis and recorded by location: pelvic disease should be classified as locoregional, and extrapelvic disease (retroperitoneal, mediastinal, thoracic, or other) as metastatic. Nodes  $\geq 1.5$  cm in the short axis are considered pathologic and measurable. As per RECIST v1.1, lymph nodes  $\geq 1.0$  and less than 1.5 cm in the short axis may be pathologic and should be recorded as non-target lesions. Nodes less than 1.0 cm in the short axis are considered nonpathologic.

**Non-measurable:**

- All other lesions, including small lesions (longest diameter  $<10$  mm or pathological lymph nodes with  $\geq 10$  to  $<15$  mm short axis at baseline).
- Truly non-measurable lesions include the following: leptomeningeal disease, ascites, pleural/pericardial effusion, inflammatory breast disease, lymphangitic involvement of skin or lung, and abdominal masses/abdominal organomegaly identified by physical examination that is not measurable by CT or MRI.
- Previously irradiated lesions or lesions subjected to other local-regional therapy.

*CONFIDENTIAL*

Study Drug: AC176

Sponsor/Development Innovations Study Number: AC176-001/GU 207

Final Protocol: 10 July 2023 Version 4.0

## **Special Consideration Regarding Lesion Measurability:**

### *Cystic lesions*

Cystic lesions thought to represent cystic metastases can be considered measurable lesions if they meet the criteria for measurability from a radiological point of view, but if non-cystic lesions are present in the same patient, these should be selected as target lesions.

## **Definition of Target and Non-Target Lesions**

### **Target lesions:**

A maximum of 5 measurable lesions (with a maximum of 2 lesions per organ), representative of all involved organs should be identified as target lesions at baseline. Pathological lymph nodes which are defined as measurable and may be identified as target lesions must meet the criterion of a short axis of  $\geq 15$  mm by CT scan. Target lesions should be selected on the basis of their size (longest diameter for non-nodal lesions or short axis for nodal lesions), but in addition should be those that lend themselves to reproducible repeated measurements. It may be the case that, on occasion, the largest lesion does not lend itself to reproducible measurement in which circumstance the next largest lesion, which can be measured reproducibly, should be selected.

A *sum of the diameters* (longest for non-nodal lesions, short axis for nodal lesions) for all target lesions will be calculated and reported as the baseline sum of diameters. If lymph nodes are selected as measurable lesions, only the short axis is added into the sum, even if the nodes regress to below 10 mm in the study. The baseline sum of diameters will be used as reference to further characterize any objective tumor regression in the measurable dimension of the disease.

### **Special cases:**

- If a target lesion has completely disappeared, the longest diameter should be recorded as 0 mm.
- If a target lesion is believed to be present and is faintly seen but too small to measure, a default value of 5 mm should be assigned. If an accurate measure can be given, this should be recorded, even if it is below 5 mm.
- When nodal disease is included in the sum of target lesions and the nodes decrease to “normal” size ( $<10$  mm), they may still have a measurement reported on scans. This measurement should be recorded even though the nodes are normal in order to not overstate progression should it be based on increase in size of the nodes.
- If a target lesion splits into two or more parts, then record the sum of the diameters of those parts. If two or more target lesions merge then the sum of the diameters of the combined lesion should be recorded for one of the lesions and 0 mm recorded for the other lesion(s).
- Similarly, as lesions coalesce, a plane between them may be maintained that would aid in obtaining maximal diameter measurements of each individual lesion. If the lesions have truly coalesced such that they are no longer separable, the vector of the longest diameter in this instance should be the maximal longest diameter for the ‘coalesced lesion’.

*CONFIDENTIAL*

Study Drug: AC176

Sponsor/Development Innovations Study Number: AC176-001/GU 207

Final Protocol: 10 July 2023 Version 4.0

### **Non-target lesions:**

All other lesions (or sites of disease) including pathological lymph nodes (those with short axis  $\geq 10$  mm but  $< 15$  mm) should be identified as non-target lesions (NTLs) and should also be recorded at baseline. Nodes that have a short axis  $< 10$  mm are considered non-pathological and should not be recorded or followed. In addition, it is possible to record multiple NTLs involving the same organ as a single item on the case record form (e.g., "multiple enlarged pelvic lymph nodes" or "multiple liver metastases").

### **Methods of Assessment**

The same method of assessment and the same technique should be used to characterize each identified and recorded lesion at baseline and during follow-up visits. All baseline evaluations should be performed as close as possible to the treatment start and never more than 4 weeks before the beginning of the treatment.

*CT, MRI:* CT scanning with IV contrast is the best currently available and reproducible method to measure lesions selected for response assessment. This guideline has defined measurability of lesions on CT scan based on the assumption that CT slice thickness is 5 mm or less. When CT scans have slice thickness greater than 5 mm, the minimum size for a measurable lesion should be twice the slice thickness. If IV contrast cannot be administered (for example, in the situation of allergy to contrast), a non-contrast CT of the chest is still preferred over MRI or chest X-ray. MRI is also acceptable and can be used when CT is not feasible or is medically contraindicated.

*Clinical lesions:* Clinical lesions will only be considered measurable when they are superficial and  $\geq 10$  mm diameter as assessed using calipers (e.g., skin nodules). For the case of skin lesions, documentation by color photography including a ruler to estimate the size of the lesion is suggested.

*X-ray:* Chest CT is preferred over chest X-ray, particularly when progression is an important endpoint, since CT is more sensitive than X-ray, particularly in identifying new lesions. However, lesions on chest X-ray may be considered measurable if they are clearly defined and surrounded by aerated lung.

*Ultrasound:* Ultrasound is not useful in assessment of lesion size and should not be used as a method of measurement. Ultrasound examination can, however, be used to identify the presence of new lesions. If new lesions are identified by ultrasound in the course of the study, confirmation by CT or MRI is advised.

*Endoscopy, Laparoscopy, Tumor markers, Cytology, Histology:* The utilization of these techniques alone will not be used for objective tumor response measurements.

*FDG-PET:* FDG-PET scans may be used as a method for identifying new lesions in the assessment of progression, according with the following algorithm: New lesions will be recorded where there is positive FDG uptake (defined as when an uptake greater than twice that of the surrounding tissue is observed) not present on baseline FDG-PET scan or in a location corresponding to a new lesion by CT/MRI at the same visit. If there is no baseline FDG-PET scan available, and no evidence of new lesions by CT/MRI then follow-up CT/MRI assessments should be continued, scheduled as per protocol or clinical indicated, in order to confirm new lesions.

*CONFIDENTIAL*

Study Drug: AC176

Sponsor/Development Innovations Study Number: AC176-001/GU 207

Final Protocol: 10 July 2023 Version 4.0

## **Tumor response evaluation**

This section provides the definitions of the criteria used to determine objective tumor response.

### *Evaluation of target lesions:*

Complete Response (CR)	Disappearance of all target lesions since baseline. Any pathological lymph nodes must have a reduction in short axis to <10 mm.
Partial Response (PR)	At least a 30% decrease in the sum of the diameters of target lesions, taking as reference the baseline sum of diameters.
Stable Disease (SD)	Neither sufficient shrinkage to qualify for PR nor sufficient increase to qualify for PD.
Progressive Disease (PD)	At least a 20% increase in the sum of diameters of target lesions, taking as reference the smallest sum on study or nadir (this includes the baseline sum if that is the smallest on study). In addition to the relative increase of 20%, the sum must also demonstrate an absolute increase of at least 5 mm.
Not Evaluable (NE)	Only relevant if any of the target lesions were not assessed or not evaluable. Note: If the sum of diameters of assessed lesions meets the progressive disease criteria, progressive disease overrides not evaluable as a target lesion response.

### *Evaluation of non-target lesions*

Complete Response (CR)	Disappearance of all non-target lesions since baseline. All lymph nodes must be non-pathological in size (<10 mm short axis).
Non-CR/Non-PD	Persistence of one or more non-target lesion(s) and/or maintenance of tumor marker level above normal limits.
Progression (PD)	Unequivocal progression of existing non-target lesions indicative of a substantial worsening in non-target disease. Unequivocal progression may be due to an important progression in one lesion only or in several lesions. In all cases the progression MUST be clinically significant for the physician to consider changing (or stopping) therapy.
Not Evaluable (NE)	Only relevant when one or some of the non-target lesions were not assessed and, in the Investigator's opinion, they are not able to provide an evaluable overall non-target lesion assessment at this visit. Note: For patients without target lesions at baseline, this is relevant if any of the non-target lesions were not assessed at this visit and the progression criteria have not been met.

To achieve “unequivocal progression” on the basis of non-target lesions, there must be an overall level of substantial worsening in non-target disease such that, even in presence of SD or PR in target lesions, the overall tumor burden has increased sufficiently to merit discontinuation of therapy. A modest “increase” in the size of one or more non-target lesions is usually not sufficient to qualify for unequivocal progression status.

*CONFIDENTIAL*

Study Drug: AC176

Sponsor/Development Innovations Study Number: AC176-001/GU 207

Final Protocol: 10 July 2023 Version 4.0

*New lesions:* The presence of one or more new lesions is assessed as disease progression. A lesion identified at a follow-up assessment in an anatomical location that was not scanned at baseline is considered a new lesion and will indicate disease progression. The finding of a new lesion should be unequivocal: i.e. not attributable to differences in scanning technique, change in imaging modality or findings thought to represent something other than tumor. If a new lesion is equivocal, for example because of its small size, the treatment and tumor assessments should be continued until the new lesion has been confirmed. If repeat scans confirm there is a new lesion, then the progression date should be declared using the date of the initial scan.

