#### Evaluation of overall response

Target lesions	Non-Target lesions	New Lesions	Overall response
CR	CR	No	CR
CR	Non-CR/Non-PD	No	PR
CR	NE	No	PR
PR	Non-PD or NE	No	PR
SD	Non-PD or NE	No	SD
NE	Non-PD or NE	No	NE
PD	Any	Yes or No	PD
Any	PD	Yes or No	PD
Any	Any	Yes	PD

CR = complete response, PR = partial response, SD = stable disease, PD = progressive disease, NE = not evaluable

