**Table 7      Overall radiological response – RECIST v1.1 and bone progression (PCWG3)**

Overall visit soft tissue response (RECIST 1.1)	Bone progression status (PCWG3)	Overall radiological response
CR	No bone lesions at baseline	CR
CR, target lesions were present at baseline	Non-PD or NE	PR
CR, only non-target lesions present at baseline	Non-PD or NE	Non-CR/Non PD
PR	Non-PD or NE	PR
SD	Non-PD or NE	SD
No soft tissue lesions at baseline	Non-PD or NE	Non-PD
PD	Any	PD
Any	PD	PD

CR = complete response, PR = partial response, SD = stable disease, PD = progressive disease, NE = not evaluable

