### On-Study Disease Assessments

- PSA results are to be collected on Day 1 of each treatment cycle
  - Continue through early rises for a minimum of 12 weeks unless there is other evidence of progression, as favorable effects on PSA may be delayed for  $\geq 12$  weeks
  - Ignore PSA rises before 12 weeks in determining PSA response

Patients with PSA progression are allowed and encouraged to continue treatment until symptomatic or radiographic progression.

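### Appendix B lets a patient with all non-target lesions gone but a raised tumor marker be both CR and Non-CR/Non-PD, so the same scans can be labelled CR or PR

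*Protocol*

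**What the plan says.** Appendix B, under the evaluation of non-target lesions, defines CR as "Disappearance of all non-target lesions since baseline", with all nodes below 10 mm in short axis. It sets no marker condition. The next row, Non-CR/Non-PD, reads "Persistence of one or more non-target lesion(s) and/or maintenance of tumor marker level above normal limits".

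The table for overall soft-tissue response then combines target and non-target results. CR with CR gives CR. The row below it is "CR Non-CR/Non-PD No PR", so target CR with non-target Non-CR/Non-PD gives PR.

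The Methods of Assessment part of the same appendix groups "Endoscopy, Laparoscopy, Tumor markers, Cytology, Histology" and says of them: "The utilization of these techniques alone will not be used for objective tumor response measurements". Table 7 merges soft tissue and bone into what its title calls a radiological response. It reserves overall CR for soft-tissue CR with "No bone lesions at baseline".

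PSA is handled separately. Appendix C states that "PSA results are to be collected on Day 1 of each treatment cycle", and Sections 7.4.2 and 7.4.3 and Appendix C give its own progression and response rules.

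**The concern.** Categories of a response scale should exclude one another. Here they do not: the and/or makes a raised marker sufficient for Non-CR/Non-PD even when no lesion remains, and the CR row does not rule that patient out. There is no order of precedence, and no normal limit for the marker is given. Two investigators reading the same scans could each follow the table and record different results.

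The marker clause also fits poorly with the rest of the appendix. Methods of Assessment says markers alone are not used for objective response, yet in this patient the marker alone moves the category. What is at stake is a reproducible CR/PR split and, in one small subgroup, whether a patient is a responder at all.

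**Working it through.** The plan gives no figure on this point, so the check is to carry one patient through the tables under both labels. The patient has all soft-tissue lesions gone, nodes below 10 mm, no new lesions, bone status Non-PD or NE where bone lesions existed at baseline, and a marker above normal.

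| Baseline disease | Non-target label CR | Non-target label Non-CR/Non-PD | Does response status (CR or PR) change? |
|---|---|---|---|
| Target and non-target, no bone lesions | Soft tissue CR; Table 7 CR | Soft tissue PR; overall PR | No, but the category does |
| Target and non-target, with bone lesions | Soft tissue CR; Table 7 PR | Soft tissue PR; Table 7 PR | No |
| Non-target soft tissue only, no bone lesions | Soft tissue CR; Table 7 CR | No matching row in either table; not CR or PR | Yes |
| Non-target soft tissue only, with bone lesions | Soft tissue CR; Table 7 Non-CR/Non-PD | No matching row in Table 7; not CR or PR | No |

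Effect on the endpoints in Section 10.4.2:

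1. ORR counts confirmed CR or PR, so the first row of the table leaves it unchanged.
2. DoR starts at the first confirmed CR or PR, so its start date is also unchanged in that row.
3. TTP, rPFS and PFS depend on progression or death. Neither label is progression, so they do not move in any row.
4. Only the third row can change ORR. Section 3.1, criterion 4, does not require measurable disease, so such patients can enrol. The synopsis and Table 3 state the ORR objective for patients with measurable disease, and Appendix B draws target lesions from measurable lesions, so a non-target-only patient falls outside that objective. Section 10.4.2, however, runs all efficacy analyses on the efficacy evaluable set, which Section 10.3 defines without that limit.
5. If these patients are counted and a Part B cohort supplies its full 30 patients, each relabelled patient shifts ORR by 1/30 = 3.3 percentage points.

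How often a marker would still be raised cannot be taken from the protocol. As illustration only, assume a normal limit of 4 ng/mL and log-normal baseline PSA with median 50 ng/mL (range 20 to 100) and log-SD 1.5 (range 1.0 to 1.5). Then P(PSA > 4) = 1 − Φ(ln(4 / (median × (1 − fall))) / SD).

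- 90% fall: 1 − Φ(ln(4/5)/1.5) = 1 − Φ(−0.15) = 0.56; range 0.24 to 0.82.
- 50% fall: 1 − Φ(ln(4/25)/1.5) = 1 − Φ(−1.22) = 0.89; range 0.73 to 0.99.

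All these inputs are assumptions. They also describe patients in general, not the few whose lesions have all disappeared.

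**The case against.** The strongest reply is that nothing the protocol lists as an endpoint moves in the population it names for ORR. CR rate is not an endpoint, CR and PR count alike, and the one subgroup where ORR could move is excluded by the measurable-disease wording of the objective. That stands, and it is why the point is minor. It does not remove the overlap, and Section 10.4.2 does not repeat the restriction.

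A second reply is that Methods of Assessment bars markers only when used alone, so a marker read together with scans is not plainly forbidden. This also stands in part: that sentence does not by itself make response imaging-only. The case for imaging rests equally on the radiological title of Table 7 and on PSA having its own endpoints. Appendix B does not name PSA in the clause either; that is an inference, though the natural one in this trial.

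Two stronger readings are tempting and should not be drawn. One is that most complete responses would disappear. Table 7 already withholds overall CR from patients with baseline bone lesions, so they have none to lose, and the illustrative share runs as low as 24%. The other is that ORR and PSA response become partly the same measurement. ORR does not change in patients with target lesions, and PSA response is a confirmed fall of at least 50% from baseline, whereas the clause concerns an absolute level.

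**Conclusion.** The two non-target definitions overlap as written, and nothing else in the protocol separates them. For patients with target and non-target disease and no baseline bone lesions, the effect is confined to the CR/PR label. For patients with only non-target soft-tissue disease and no bone lesions, it is CR against no response, and it reaches ORR only if the denominator is the whole efficacy evaluable set. Response status in patients with baseline bone lesions is unaffected. The number of patients involved cannot be derived from the protocol. The conclusion rests on reading the tumor marker as PSA and on taking the and/or at face value. Severity is minor: a wording defect in an appendix that bears on descriptive secondary results.

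**What to change.** In Appendix B, end the Non-CR/Non-PD definition after the persistence of non-target lesions and delete the tumor-marker alternative. The two rows then exclude each other, and the overall response is radiological, in line with Methods of Assessment and Table 7. Report PSA only through Section 7.4.3 and Appendix C.

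The cost is one deleted clause, with no added data, visits or patients. The published criteria that the protocol adopts are not among the documents, so the sponsor should confirm that the deletion agrees with them. If the marker is to be kept, the alternative is to add its normalisation, with a stated limit, to non-target CR and to reconcile Methods of Assessment. That also removes the overlap but needs more changes. Either choice should be made before responses are tabulated.
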